### **2.1.3 Exploratory Efficacy Objective**

The exploratory efficacy objective for this study is to further assess the efficacy of ocrelizumab 600 mg IV given every 24 weeks by monitoring patient-reported outcomes (PROs) related to quality of life (QoL), treatment satisfaction and other endpoints or analyses as follows:

- Multiple Sclerosis Impact Scale (MSIS)-29 (MS-specific QoL questionnaire)
- Treatment satisfaction questionnaire for medication (TSQM II)
- Patient reported outcome: SymptoMScreen
- MRI and clinical outcomes at 6 months and 1 year
- Predictors of NEDA and association between NEDA and disability or other efficacy parameters
- Severity of relapses (hospitalization for MS relapse, use of corticosteroids, residual disability)
- Employment status (WPAl)
- Proportion of patients who have NEDA, as per protocol defined events during a 96-week period and starting from baseline

## **2.2 SAFETY OBJECTIVE**

The safety objective for this study is to evaluate the safety and tolerability of ocrelizumab 600 mg IV given every 24 weeks on the basis of the following endpoints:

- Rate and nature of adverse events
- Changes in vital signs, physical and neurological examinations, clinical laboratory results, locally reviewed MRI for safety (non-MS CNS pathology) and concomitant medications (including pre-medications and medications used during and following ocrelizumab administration).

## **3. STUDY DESIGN**

### **3.1 DESCRIPTION OF THE STUDY**

This study is a prospective, multicenter, open-label, efficacy and safety study in patients with RRMS who have had a suboptimal response to an adequate course of a DMT. An adequate course of prior DMT is defined as a stable dose of the same DMT administered for at least 6 months. The first dose of ocrelizumab will be administered as an initial dose of two 300-mg infusions (600 mg total) in 250 mL 0.9% sodium chloride

each separated by 14 days (i.e., Days 1 and 15) followed by one 600-mg infusion in 500 mL 0.9% sodium chloride every 24 weeks for the remainder of the study duration.

This study will enroll 750 patients. Patients will be assessed for efficacy and safety every 24 weeks as described in the Schedule of Assessments presented in [Appendix 1](#).

The study will consist of the following periods:

- Screening period: Up to 4 weeks
- Treatment period: Open-label treatment period of 96 weeks (last dose administered at Week 72)
- A follow-up period of at least 2 years, which is independent of the DMT administered

Follow-up Period: Patients who discontinue treatment early will be followed up for at least 96 weeks after the Early Treatment Discontinuation Visit. Patients who complete the 96 weeks Treatment Period and, in agreement with their treating neurologist, decide not to continue in a separate long-term extension (LTE) study, will be followed up for at least 96 weeks after the end of the Treatment Period. Patients who decide to leave the study and switch to commercially marketed Ocrelizumab, either after completion of the 96 weeks Treatment Period or after early discontinuation of the 96 weeks Treatment Period, will not enter the safety Follow-up Period.

[figure not shown]
Patients whose B-cells have not been repleted after 96 weeks of Follow-up Period will continue with visits every 24 weeks, and telephone contacts every 8 weeks, until B-cell repletion (Prolonged B-cell monitoring). If the patients are receiving other B-cell targeted therapies, then the Follow-up Period will be stopped at 96 weeks regardless of their B-cell count.

A structured telephone interview will be conducted by site personnel every 8 weeks between the study visits during the treatment period and follow-up to identify and collect information on any changes in the patient's health status that warrant an unscheduled visit (including new or worsening neurological symptoms) and possible events or infections.

### 3.1.1 Overview of Study Design

Figure 2 presents an overview of the study procedures. A schedule of assessments is provided in [Appendix 1](#).

**Figure 2 Overview of Study Procedures**

DMTs=disease modifying treatments; IV=intravenous; RRMS=relapsing remitting multiple sclerosis.

### 3.1.2 Screening

Patients screened for this study should not be withdrawn from DMT therapies for the sole purpose of meeting eligibility for the trial. Patients who discontinue their current therapy for non-medical reasons should be informed of treatment options before deciding to enroll in the study. Investigators should refer to the local label for discontinuation/wash out of previous DMTs. The summary of product characteristics (SmPCs) of DMTs for EMEA countries are provided in [Appendix 8](#).

After providing written informed consent, patients will enter a screening period (up to 4-weeks) to be evaluated for eligibility.

Re-screening of patients is allowed in this protocol. In case a patient needs to be re-screened there is no need to sign a new ICF if the re-screening is done within 2 months after signing the ICF; the patients should only be asked to re-sign and re-date the previously signed ICF to confirm that they are still willing to participate in the study.

### 3.1.3 Treatment Period

Eligible patients will be treated with an initial dose of two 300-mg infusions (600 mg total) in 250 mL 0.9% sodium chloride each separated by 14 days (i.e., Days 1 and 15) followed by one 600-mg infusion in 500 mL 0.9% sodium chloride every 24 weeks for the remainder of study duration.

Laboratory samples can be taken up to 2 weeks prior to the scheduled study visit. Results should be available prior dosing, except for John Cunningham virus (JCV) and immunoglobulins (Ig) (plasma samples collected and stored centrally), which will be analyzed upon request and CD8 and CD19 (no interference with re-treatment).

For patients presenting with EDSS change at Week 96, the EDSS score will be confirmed after a further 24 weeks.

#### Criteria for Re-Treatment with Ocrelizumab

Prior to re-treatment with ocrelizumab, patients will be evaluated for the following conditions and laboratory abnormalities. If any of these are present prior to re-dosing, further administration of ocrelizumab should be suspended until these are resolved or held indefinitely:

[figure not shown]
- Life threatening (Common Terminology Criteria for Adverse Events [CTCAE] Grade 4) infusion-related event that occurred during a previous ocrelizumab infusion
- Any significant or uncontrolled medical condition or treatment-emergent, clinically significant laboratory abnormality
- Active infection other than a fungal nailbed infection. The re-treatment should be delayed until the active infection is treated, and patient fully recovered
- CD4 cell count < 250/ $\mu$ L
- Ongoing pregnancy

At the end of the study treatment the patients will be encouraged to be included in a separate LTE study to further evaluate the efficacy and safety of their DMT treatment and this is independent of the DMT. This LTE will also aim to evaluate the relationship between the primary endpoint of this study and long-term outcome.

Patients who discontinue treatment early will be followed up for at least 96 weeks after the Early Treatment Discontinuation Visit. Patients who complete the 96 weeks Treatment Period and, in agreement with their treating neurologist, decide not to continue in a separate LTE study, will be followed up for at least 96 weeks after the end of the Treatment Period (see [Section 3.1.4](#)). Patients who decide to leave the study and switch to commercially marketed Ocrelizumab, either after completion of the 96 weeks Treatment Period or after early discontinuation of the 96 weeks Treatment Period, will not enter the safety Follow-up Period.

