#### **4.6.2 Study Treatment Discontinuation**

Patients must discontinue study treatment if they experience any of the following:

- Ongoing pregnancy or breastfeeding (in case of pregnancy, treatment should be interrupted, and the patient should be monitored for safety; however, the patient can be re-started with the treatment after the pregnancy and breastfeeding period. During pregnancy and breastfeeding, the patient will continue to come for the regular schedule visits as per protocol and will perform all assessments except MRI).
- Life-threatening IRR or serious hypersensitivity reaction
- Active hepatitis B infection
- PML
- Active tuberculosis, either new onset or reactivation

The primary reason for study treatment discontinuation should be documented on the appropriate eCRF. Patient discontinuing the study treatment prematurely will be further monitored in a safety follow-up (see [Section 3.1.4](#)).

Patients who discontinue study treatment prematurely will not be replaced.

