**Table 2 Guidelines for Management of Specific Adverse Events**

Event	Action to Be Taken
Mild to moderate IRR	

• If the event that a patient experiences is a mild to moderate IRR (e.g. headache), the infusion rate should be reduced to half the rate at the time of the event.

• This reduced rate should be maintained for at least 30 minutes. If tolerated, the infusion rate may then be increased according to the patient's initial infusion schedule.

Severe IRR (or complex of flushing, fever, and throat pain)	

• If a patient experiences a severe IRR or a complex of flushing, fever, and throat pain symptoms, the infusion should be interrupted immediately, and the patient should receive symptomatic treatment.

• The infusion should be re-started only after all symptoms have resolved.

• The initial infusion rate at restart should be half of the infusion rate at the time of onset of the reaction.

Life-threatening or disabling IRR (e.g., anaphylaxis)	

• Immediately stop ocrelizumab if there are signs of a life-threatening or disabling IRR during an infusion, such as acute hypersensitivity or acute respiratory distress syndrome.

• The patient should receive appropriate treatment.

• Permanently discontinue ocrelizumab in these patients.

hr=hour; IRR=infusion-related reaction

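### Protocol 3.1.3 leaves re-dosing open after a life-threatening infusion reaction, where 4.6.2 and Table 2 require discontinuation, and the three places label the event differently

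*Protocol*

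**What the plan says.** Three places in the current protocol text deal with a life-threatening reaction to an infusion.

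- **Section 3.1.3, Criteria for Re-Treatment with Ocrelizumab.** If any of five conditions is present before re-dosing, "further administration of ocrelizumab should be suspended until these are resolved or held indefinitely". The first condition is "Life threatening (Common Terminology Criteria for Adverse Events [CTCAE] Grade 4) infusion-related event that occurred during a previous ocrelizumab infusion". The others are an uncontrolled medical condition or significant laboratory abnormality, active infection, a low CD4 count and pregnancy.
- **Section 4.6.2, Study Treatment Discontinuation.** The lead-in is "Patients must discontinue study treatment if they experience any of the following", and the list includes "Life-threatening IRR or serious hypersensitivity reaction". A return to treatment is described for one item only, pregnancy and breastfeeding: "the patient can be re-started with the treatment after the pregnancy and breastfeeding period".
- **Section 5.1.4, Table 2.** In the row for the most severe IRRs: "Immediately stop ocrelizumab if there are signs of a life-threatening or disabling IRR during an infusion", and then "Permanently discontinue ocrelizumab in these patients".

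Two further places bear on how these are read. Table 3 in Section 5.3.3 is the severity scale that the protocol applies to IRRs. Table 1 in Section 4.3.2.1 requires a clinical check of eligibility before each next infusion, and the text under it points to Section 5.1.4 for rules on modifying, interrupting or stopping treatment. The SAP does not restate or settle the rule.

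**The concern.** One kind of event appears under an open rule in one section and under closed rules in two others. Section 3.1.3 is the text a site would naturally consult when deciding whether to give the next dose, because it is headed as the re-treatment criteria and Table 1 requires that check. It gives two alternatives for a mixed list, assigns neither to the infusion-event item, and does not refer the reader to 4.6.2 or 5.1.4. It also says should, where 4.6.2 says must.

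What is at stake is conduct after a life-threatening reaction. Two sites, each relying on a section of the same protocol, could handle the same patient differently. For one patient the consequence could be serious, even though few patients would be affected.

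**Working it through.** No sample-size or power figure is involved, so the main check is a comparison of the texts.

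**Step 1. Set the rules side by side.**

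| Place | Event label | Instruction | Return to treatment |
|---|---|---|---|
| 3.1.3 | Life-threatening, CTCAE Grade 4 | Suspend until resolved, or hold indefinitely | Left open by the first alternative |
| 4.6.2 | Life-threatening IRR | Must discontinue | Described for pregnancy and breastfeeding only |
| Table 2 (5.1.4) | Life-threatening or disabling IRR | Stop at once, discontinue permanently | None |

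One place leaves re-dosing open. Two require discontinuation, and one of those two says it is permanent.

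**Step 2. Can the first alternative apply to the infusion-event item?** Under Table 1, infusions fall on Day 1, Day 15, Week 24, Week 48 and Week 72. From Day 15 onward the next infusion is many weeks away. Section 5.1.1.1 describes IRRs as arising within 24 hours of an infusion. An acute reaction may well be over by the next dosing visit, and a reader could then take the until-resolved condition as met. The active-infection item carries its own instruction on when dosing may restart; the infusion-event item carries none.

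**Step 3. Does the protocol state permanence where it intends it?** It does so in Section 5.1.1.2, for confirmed progressive multifocal leukoencephalopathy and for an infusion during which hypersensitivity is suspected, and in Table 2. Section 3.1.3 does not.

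**Step 4. Compare the event definitions with Table 3.** Table 3 places disabling reactions in Grade 3. Its Grade 4 covers life-threatening consequences and also reactions needing urgent intervention. Two mismatches follow:

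- A disabling Grade 3 IRR falls under the Table 2 row but outside the Grade 4 item in 3.1.3.
- An IRR graded 4 only because urgent intervention was needed has the Grade 4 label of 3.1.3, but it is unclear whether it counts as life-threatening for 4.6.2 or Table 2.

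**Step 5. Size for the primary analysis.** SAP 4.4.1 excludes from the NEDA (no evidence of disease activity) analysis a patient who stops treatment early without disease activity, for a reason other than death or lack of efficacy. A suspended and re-dosed patient would stay in. A patient with earlier disease activity counts as NEDA = No either way. Take the planned 750 patients and 30% NEDA, that is 0.30 × 750 = 225 patients:

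- The patient would have stayed event-free: 225/750 = 30.00% if retained, 224/749 = 29.91% if excluded. The difference is 0.09 points.
- The patient would later have had an event: 225/750 = 30.00% if retained, 225/749 = 30.04% if excluded. The difference is 0.04 points.
- Simple upper bound per patient: 1/750 = 0.13 points.

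The planned 95% CI half-width is 3.3 points (Protocol 6.1).

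**The case against.** The strongest reply is that the three places can all be obeyed at once. An indefinite hold satisfies 3.1.3, 4.6.2 and Table 2 together. The infusion-event item also describes a past occurrence ("infusion-related event that occurred during a previous ocrelizumab infusion"), which cannot be undone, so the second alternative is arguably the one meant for it. The text under Table 1 sends the reader to 5.1.4 for stopping rules. Table 2 takes effect during the infusion itself, so a site that follows it has already ended treatment before the re-treatment check arises.

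Much of this stands, and it limits the point:

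- A reader might infer that 3.1.3 instructs or authorises re-dosing after a Grade 4 event. It does not; it fails to rule it out.
- A reader might infer that both other sections demand permanent discontinuation. Only Table 2 uses that word. Section 4.6.2 says must discontinue, in a list where one item, pregnancy, allows a return to treatment.

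The reply does not remove the inconsistency. That a careful reader can find a course satisfying all three places does not mean that the re-treatment checklist states it. The pointer to 5.1.4 sits under the dosing table, not in 3.1.3. The reply also leaves the differing event labels untouched.

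**Conclusion.** The point holds as an internal inconsistency in current protocol text. Section 3.1.3 leaves re-dosing open after a life-threatening infusion reaction, where 4.6.2 and Table 2 require discontinuation, and the three places do not define the event in the same way or in line with Table 3. The grounds are patient safety and uniform conduct across sites.

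Frequency is expected to be low. The background on clinical safety in Section 1.2 reports one Grade 4 serious IRR on ocrelizumab in the two pooled relapsing-MS trials. It also reports five patients with a serious IRR on ocrelizumab in the primary-progressive trial, without grades.

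A reader might also infer that inconsistent handling would bias the primary result, because it changes who is excluded under SAP 4.4.1. The route exists, but its size does not support that reading: at most about 0.13 points per patient against a half-width of 3.3. This assumes roughly the planned 750 patients in the analysis and only isolated events.

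No view is taken here on which clinical rule is right.

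**What to change.** Reconcile Section 3.1.3, Section 4.6.2 and Table 2 so that one rule and one event definition apply to life-threatening infusion reactions. Specifically:

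1. In 3.1.3, state which alternative applies to which of the five conditions.
2. Use one event label in all three places, aligned with the Table 3 grades, and say explicitly how disabling Grade 3 reactions and Grade 4 reactions defined by urgent intervention are handled.
3. Add a cross-reference from 3.1.3 to 4.6.2 and 5.1.4.

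The sponsor's clinical team decides the content of the rule. The cost is a few lines of wording in the next amendment or a clarification letter to sites, with whatever approval Section 9.6 requires. Sample size, visit schedule and planned analyses do not change.

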**Figure 3 Overview of End of Treatment Period**

### **3.1.4 Follow-up Period**

[figure not shown]
Patients who discontinue treatment early will be followed up for at least 96 weeks after the Early Treatment Discontinuation Visit. Patients who complete the 96 weeks Treatment Period and, in agreement with their treating neurologist, decide not to continue in a separate LTE study, will be followed up for at least 96 weeks after the end of the Treatment Period.

Patients who decide to leave the study and switch to commercially marketed Ocrelizumab, either after completion of the 96 weeks Treatment Period or after early discontinuation of the 96 weeks Treatment Period, will not enter the safety Follow-up Period.

Any patient whose peripheral blood B-cell count remains depleted after this period will continue to be monitored at 24-week intervals until the B-cell count has returned to the baseline value or to lower limit of normal (LLN) range, whichever is lower.

[Figure 4](#) provides an overview of the Follow-up Period, which is the variable B-cell monitoring period. A schedule of assessments for the Follow-up Period is presented in [Appendix 2](#).

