## **3.2 END OF STUDY AND LENGTH OF STUDY**

The end of the study treatment period has been defined as the date on which the last patient receiving the full study treatment reached the 96-week visit. Exception will be made for patients that have EDSS change at Week 96 and need confirmation of EDSS score after a further 24 weeks.

The end of the study is defined as the last patient last visit in the B-cell monitoring of the Follow-Up period. At the end of the study treatment, patients will be encouraged to be included in a separate LTE study to further evaluate the efficacy and safety of their DMT treatment, and this is independent of the DMT. This LTE will also aim to evaluate the relationship between the primary endpoint of this study and long-term outcome.

The total length of the study, from screening of the first patient to the end of the study, is expected to be approximately 5 years. This includes an enrollment period of approximately 12 months.

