- j Plasma samples for anti-JCV antibodies should be taken at baseline and repeated yearly and end of study for storage in a central laboratory. Samples will be analyzed upon request.
- k Patients must have an EDSS score of 0.0 to 4.0 points, inclusive at screening to be eligible. EDSS needs to be confirmed after 24 weeks if EDSS changes from baseline to Week 96
- l Neurological examinations will be used to distinguish relapse in MS from another neurological (non-MS) disorder. Potential relapses should be recorded throughout the treatment period. Investigators will also screen patients for signs and symptoms of PML by evaluating neurological deficits localized to the cerebral cortex, such as cortical symptoms/signs, behavioral and neuropsychological alteration, retrochiasmal visual defects, hemiparesis, cerebellar symptoms/signs (e.g., gait abnormalities, limb incoordination). Patients with suspected PML should be withheld from ocrelizumab treatment until PML is ruled out by complete clinical evaluation and appropriate diagnostic testing. A patient with confirmed PML should be withdrawn from the study.
- m After initiation of study drug, all adverse events should be reported until 96 weeks after the end of the Treatment Period but may be extended in patients whose B-cells take longer to replete. After this period, the investigator should report any serious and non-serious adverse events that are believed to be related to prior study drug treatment (see Sections [5.3.1](#) and [5.6](#)).
- n All patients must receive prophylactic treatment with 100 mg methylprednisolone, administered by slow IV infusion, to be completed approximately 30 minutes before the start of each ocrelizumab infusion, and an antihistaminic drug (e.g., diphenhydramine) approximately 30 – 60 minutes before each infusion of ocrelizumab.
- o Ocrelizumab will be administered as two 300-mg IV infusions in 250 mL 0.9% sodium chloride each on Days 1 and 15 and one 600-mg infusion in 500 mL 0.9% sodium chloride every subsequent dose (i.e., every 24 weeks) for a maximum of 72 weeks. It is anticipated that the patient will need to stay at the hospital or clinic for a full day for the infusion visits.

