## Appendix 2: Follow-up Schedule of Assessments

(Including Additional B-Cell Monitoring, if required)

Patients who decide to leave the study and switch to commercially marketed Ocrelizumab, either after completion of the 96 weeks Treatment Period or after early discontinuation of the 96 weeks Treatment Period, will not enter the safety Follow-up Period.

	Follow Up	Prolonged B-Cell Monitoringa
Assessment	Visits Every 24 Weeks (± 14 days) b	Visits Every 24 Weeks (± 14 days)
Routine safety laboratory tests c	X	X
Lymphocytes subtypes d	X	X
Plasma anti-JCV antibodies sample e	X	X
Vital signs	X	X
EDSS score f	X	
Potential relapses recorded	X	X
Adverse events g	X	X
BICAMS assessment h	X	X
Concomitant medication	X	X
MRI i	X	X
Telephone contact every 8 weeks j	X	X

BICAMS= Brief International Cognitive Assessment for Multiple Sclerosis; EDSS = Expanded Disability Status Scale; JCV = John Cunningham virus; MRI = Magnetic resonance imaging; MS = Multiple sclerosis

- a Patients whose B-cells have not been repleted after 96 weeks of Follow-up Period will continue with visits every 24 weeks (± 14 days) and telephone contacts every 8 weeks until B-cell repletion (Prolonged B-cell monitoring). If the patients are receiving other B-cell targeted therapies, then the Follow-up Period is only 96 weeks regardless of their B-cell count.
- b Visits will be performed at 24-week intervals following the Early Treatment Discontinuation Visit (if discontinued early) or after the end of the Treatment Period
- c Routine safety lab: hematology, chemistry and urinalysis.
- d Lymphocytes subtypes samples for CD19+ and T-cell counts (CD4+, CD8+)
- e Plasma sampling for anti-JCV antibodies will be repeated yearly. Samples will be analyzed upon request.
- f EDSS assessment needs to be performed only once, at the first follow-up visit
- g After initiation of study drug, all adverse events must be reported until 96 weeks after the end of the Treatment Period, but may be extended in patients whose B-cells take longer to replete. Related SAEs must be collected and reported regardless of the time elapsed from the last study drug administration, even if the study has been closed (see Sections [5.3.1](#) and [5.6](#)).

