1. A sustained change in EDSS for a minimum of 24 weeks (-2 weeks) from the initial progression event i.e. the change in EDSS must be sustained at all available (scheduled or unscheduled) visits for a minimum of 24 weeks ($\geq 168-14$ days= 154 days) after initial progression. An “Early Discontinuation” visit can be used as a confirmation visit if it falls into the visit window (defined in the protocol) of any scheduled visit. The EDSS assessments (if any) between the initial disability progression and the confirmation of disability progression should be at least as high as the minimum change required for progression.
2. Scheduled visits within 30 days after the onset of a clinical relapse that meets conditions 1, 2 and 3 of a protocol-defined relapse definition cannot be used for confirmation of disability progression. The confirmation of the disability progression must then be based on the EDSS assessment at the next scheduled visit (which is not within 30 days of a protocol defined relapse).
3. If a patient has a missing assessment at the scheduled visit taking place at 24 weeks (≥ 154 days) after an initial progression, the confirmation of the disability progression must be based on the assessment at the next scheduled visit.

For the patients who have the initial progression at week 96 and roll over to the long term extension of Ocrelizumab study, a confirmation EDSS assessment will be collected in the long term extension (Liberto) study.

Patients who complete the treatment period without confirmed progression of disease will be censored at the date of their last EDSS assessment during the treatment period. Patients with an initial assessment of disease progression who subsequently discontinue

from the study without further assessments will not be considered to have confirmed disease progression, if the discontinuation reason is not lack of efficacy or death. Patients who discontinue from the study due to lack of efficacy or death without confirmed progression of disease will be imputed as having an event (i.e., CDP) at the time of discontinuation.

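### Completers who leave for commercial ocrelizumab have no described source for the required 24-week EDSS confirmation, and the SAP scores their unconfirmed late rise as no progression

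*Protocol*

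**What the plan says.** **The confirmation requirement applies to everyone.**
- Protocol 3.1.3: "For patients presenting with EDSS change at Week 96, the EDSS score will be confirmed after a further 24 weeks".
- Protocol 3.2, on the end of the treatment period: "Exception will be made for patients that have EDSS change at Week 96 and need confirmation of EDSS score after a further 24 weeks".
- Protocol Appendix 1, footnote k: "EDSS needs to be confirmed after 24 weeks if EDSS changes from baseline to Week 96".

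**Two sources of that EDSS are described.**
- The Follow-up Period. Appendix 2, footnote f: "EDSS assessment needs to be performed only once, at the first follow-up visit".
- The extension study. For patients who roll over with an initial progression at Week 96, SAP 4.4.1 says that "a confirmation EDSS assessment will be collected in the long term extension (Liberto) study".

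**One group reaches neither.** The sentence in Protocol 3.1.4 that begins "Patients who decide to leave the study and switch to commercially marketed Ocrelizumab" covers both completers and early discontinuers, and it ends by keeping both out of follow-up: after naming completion of the 96 weeks, it continues with "after early discontinuation of the 96 weeks Treatment Period, will not enter the safety Follow-up Period".

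**How the SAP scores an unconfirmed rise (4.4.1).**
- Confirmation needs an EDSS at least 154 days (168 - 14) after the initial rise.
- Completers without confirmed progression are censored at their last EDSS.
- Patients with an initial progression who then discontinue "from the study without further assessments will not be considered to have confirmed disease progression", unless the reason is lack of efficacy or death.
- A patient with none of the four component events is NEDA=Yes.
- The rule excluding patients whose activity status is unknown applies to treatment discontinuation before Week 96.

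**The concern.** Twenty-four-week CDP is one of the four components of the primary endpoint. A rise first seen at Week 96 can be confirmed only after Week 96. For a completer who moves to commercial drug, one rule demands the assessment and another removes the patient from the visit that would supply it. A site following 3.1.4 alone would not obtain the EDSS.

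The SAP then resolves the missing information in the favourable direction. That is at odds with its own principle for early discontinuers, who leave the analysis because their status is unknown. Whether a late rise is tested would depend on the patient's exit route rather than on the disease.

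The gap would also be hard to see in the report. The disposition summary in SAP 4.2 counts patients entering follow-up and patients rolling over, but has no line for completers who leave for commercial drug.

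**Working it through.** **1. The plan's own precision.** Inputs from Protocol 6.1: N = 750, NEDA 30%, exact Clopper-Pearson 95% interval.
- 225/750 gives 26.74% to 33.42%, half-width 3.34 points.
- 375/750 gives 46.36% to 53.64%, half-width 3.64 points.

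Both agree with the stated 3.3% and 3.6% after rounding.

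**2. Which rises need an EDSS after Week 96?** Week 96 is day 672, and 672 - 154 = 518, or Week 74. A rise first seen after about Week 74 cannot be confirmed by Week 96. Scheduled EDSS visits are at Weeks 24, 48, 72 and 96. At nominal timing a Week 72 rise is confirmable at Week 96 (168 days). With windows of ±14 days at both visits the gap runs from 140 to 196 days, so some Week 72 rises also miss the 154-day minimum.

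**3. Does any other described visit help?** Protocol 3.1.4 asks for a clinic visit directly before an alternative MS treatment starts. It is a follow-up visit timed to the treatment switch, not to 24 weeks after Week 96, so it does not fill the gap.

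**4. Do the sensitivity analyses help (SAP 4.4.4)?** A removes patients who stopped treatment before Week 96. B moves the MRI baseline, C changes the relapse definition, D restarts relapse counting at Week 8, and E imputes Gd lesions on post-infusion scans. None changes the handling of an unconfirmed EDSS rise in a completer.

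**5. Size, from progression risk.** These inputs are assumptions, because the documents do not give them:
- progressions spread evenly over the four visits, so 25% are first seen at Week 96;
- 20% to 50% of completers leave for commercial drug;
- two-year CDP risk c of 5% to 10%.

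Share of CDP events lost: 0.25 × 0.20 to 0.25 × 0.50 = 5% to 12.5%.

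Understatement of CDP: 5% × 5% = 0.25 points, to 12.5% × 10% = 1.25 points.

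Only patients with no relapse and no MRI event shift NEDA. If the components are independent and NEDA is 30%, the share with no other event is 0.30/(1 - c), which is 31.6% at c = 5% and 33.3% at c = 10%.

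Overstatement of NEDA: 0.25 × 0.316 = 0.08 points, to 1.25 × 0.333 = 0.42 points. That is about 0.6 to 3 of 750 patients.

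**6. Size, from a direct grid.** Let s be the share leaving for commercial drug, and q the share of those with a Week 96 rise that would confirm and no other event. Both are assumed. Overstatement of NEDA is 100 × s × q points.

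| s | q | Points | Patients of 750 |
|---|---|---|---|
| 5% | 0.5% | 0.025 | 0.19 |
| 20% | 1% | 0.2 | 1.5 |
| 30% | 2% | 0.6 | 4.5 |
| 30% | 4% | 1.2 | 9 |

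In the last row, moving 9 patients out of the numerator changes the interval from 26.7%-33.4% to 25.6%-32.2%. That row is a ceiling. Under step 5, q = 0.25 × c × 0.30/(1 - c), and q = 4% requires c/(1 - c) = 0.533, a two-year CDP risk of about 35%. With c of 5% to 10%, q is about 0.4% to 0.8%.

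**The case against.** The strongest reply is that confirmation is already required. Sections 3.1.3 and 3.2 and Appendix 1 footnote k demand it, Protocol 6.4.4 times the analysis after the last CDP and CDI confirmation visit, and 3.1.4 exempts switchers only from a period described as safety follow-up. This stands. A reader might infer that a Week 96 rise in a switcher can never be confirmed, or that the plan chose to forgo confirmation; the documents do not say so. What remains is that no source of the assessment is described for these patients.

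Other replies that hold in part:
- **Scoring.** A reader might infer that every such patient becomes NEDA=Yes. That needs no relapse and no MRI event, and a study exit not recorded as lack of efficacy or death. A late rise found at a relapse visit would usually qualify as a protocol-defined relapse, so that patient is already NEDA=No.
- **True negatives.** Some Week 96 rises would not persist, and for them CDP=No is correct. This limits the size of the bias but does not reverse it.
- **The Version 5 wording.** A reader might infer that the amendment created this loss. The amendment rationale calls the text a clarification, and patients could always withdraw under 4.6.1. Any completer lost after Week 96 raises the same scoring question.
- **Figure 3.** The end-of-treatment overview was not shown in the text reviewed. If it contains a confirmation visit for switchers, the text of 3.1.4 should say so.
- **Routing.** Protocol 3.1.3 and 4.3.5 steer patients towards the extension, where the EDSS is collected. That may make the affected group small, but the documents do not give its size.

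**Conclusion.** The conflict is real and should be resolved. The protocol requires a 24-week confirmatory EDSS without exception, while 3.1.4 takes completers who leave for commercial drug out of follow-up and nothing else supplies the assessment. The SAP's default then turns an unknown CDP status into CDP=No, and into NEDA=Yes when no other event occurred.

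For the primary endpoint the bias runs one way: it can only raise NEDA and lower CDP. CDI uses the same derivation (SAP 4.4.2.4), so unconfirmed late improvements are lost as well.

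The size cannot be derived from the documents. It is probably well under 1 percentage point on NEDA: about 0.08 to 0.42 points under the assumed switching share, CDP risk, even spread over visits and independence of components. Positive association between CDP and relapse or MRI activity would make it smaller. If no patient with a late CDP had another event, the same inputs give at most 1.25 points. This does not threaten the conclusions of a descriptive single-arm study, but it is avoidable and cheap to correct.

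**What to change.** 1. **Protocol.** Reconcile 3.1.4 (and the matching text in 3.1.3, 4.6.4 and the appendices) with the confirmation rule in 3.1.3, 3.2 and Appendix 1 footnote k, by stating how the already-required 24-week EDSS is obtained for completers who leave for commercial drug.
2. **SAP 4.4.1.** State that a completer with an initial progression and no EDSS at least 154 days later has unknown CDP status. Score NEDA=No if another component event occurred. Otherwise exclude the patient under the principle already applied to event-free early discontinuers.
3. **SAP 4.4.4 and 4.2.** Add one sensitivity analysis counting these patients as CDP=Yes and NEDA=No, and tabulate their number by exit route: extension, follow-up, commercial drug.

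The cost is one already-promised assessment in a few patients and a few sentences in the SAP. If patients have already left, items 2 and 3 still work without new data. The denominator and the NEDA figure fall slightly. With 3 such patients among 225 NEDA of 750, exclusion gives 222/747 = 29.7% and counting them as events gives 222/750 = 29.6%, against 30.0%. Exclusion also drops some patients whose rise would not have persisted, so the two analyses should be reported together.
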